7. RATIONALE AND BACKGROUND

AD, also known as atopic eczema, is the most common chronic inflammatory skin disease. AD is characterized by intense itching and recurrent eczematous lesions (1). AD was originally thought to affect primarily preschool children, with prevalence up to 25%, but recent evidence shows that AD in adults has an estimated prevalence of 7–10% (2). AD has a strong genetic component, is associated with atopic co-morbidities including asthma, allergic rhinitis, and food allergies, and coincides with an increased risk of other inflammatory diseases, such as arthritis and inflammatory bowel disease. AD confers a substantial burden to patients and their families, resulting in high healthcare costs. AD has been linked to psychological disturbances and reduced educational attainment (2, 3). Severe and active AD is associated with an increased risk of cardiovascular morbidity (4-6) and with certain types of malignancies (7).

Abrocitinib is a selective Janus Kinase (JAK) 1 inhibitor. The inhibition of JAK1 is thought to modulate multiple cytokines involved in the pathophysiology of AD including interleukin (IL)-4, IL-13, IL-31, IL-22, and interferon gamma. The important identified and potential risks were adopted based on non-clinical and clinical data from abrocitinib development program and from understanding of data from other JAK inhibitors (i.e., tofacitinib, baricitinib, upadacitinib). The important identified risks include VTE and herpes zoster. The important potential risks include serious and opportunistic infections, malignancy major adverse cardiovascular event (MACE), myopathy (including rhabdomyolysis), gastrointestinal perforation, and impaired bone growth and development in patients in patients aged <12 years if used off-label, and fractures. (8). Finally, embryofetal toxicity following exposure in utero is included as a potential risk. Although abrocitinib is contraindicated for use in pregnancy, the patient population will include women of childbearing potential and off-label incidental/unintended exposure during pregnancy could occur (8). Abrocitinib received marketing authorization for EU on 09 December 2021 for the treatment of moderate to severe AD in adults who are candidates for systemic therapy (8). On 21 March 2024, the indication for abrocitinib marketing authorization for the EU was expanded to adolescents 12 years and older.

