8.2. Research objectives

The study objectives are to evaluate, to the extent measurable in the available routinely collected data, indicators of HCPs' adherence to the RMMs in accordance with the abrocitinib SmPC, prescriber's brochure and DHPC, specifically:

- Indicators of adherence to performing laboratory tests of CBC, lipid panel, hepatitis B/C and TB screening prior to initiation of abrocitinib treatment,
- Indicators of adherence to performing laboratory tests of CBC and lipid panel at week 4 (± 2 week) after initiation of abrocitinib treatment,
- Indicators of adherence to consideration of risk factors for VTE, MACE, malignancy excluding NMSC, NMSC, and serious infection prior to treatment with abrocitinib,
- Indicators of adherence to avoid live attenuated vaccines immediately prior to and during treatment with abrocitinib,
- Indicators of adherence to contraindications for use during pregnancy,
- Indicators of adherence to contraindications for use among patients with severe hepatic impairment,
- Indicators of adherence to no use in patients aged < 12 years, and
- Indicators of adherence to recommended posology (estimated average daily dose).

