9.2.1. Inclusion criteria

All patients with at least 1 dispensing of abrocitinib between study start (country-specific aRMM distribution [01 Mar 2022, Sweden; 09 Mar 2022, Denmark; 31 Jul 2022, France; 30 Jan 2023, Spain; 05 April 2024, Hungary]) and December 2026 in the participating databases will be eligible for inclusion in this study. The date of the first dispensing of abrocitinib will be the index date. Patients must meet the above inclusion criteria to be eligible for inclusion in the study.

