3) The proportion of patients with evidence of having risk factors and the number of risk factors for VTE, MACE, malignancy excluding NMSC, NMSC, and serious infection (including age 65 years or older, estimated dose of >100 mg/day for patients ages 65 or older, history of atherosclerotic disease, malignancy, pregnancy, history of VTE, use of combined hormonal contraceptives or hormone replacement therapy, major surgery, inherited coagulation disorder, diabetes, history of serious or opportunistic infection, TB) within 6 months prior to initiation of treatment with abrocitinib

4) The count and proportion of patients with evidence of having received live attenuated vaccines (e.g., measles, mumps, rubella) 4 weeks prior to and during treatment with abrocitinib

5) The count and proportion (among all pregnant women identifiable in a given database) of women in whom pregnancy overlaps with abrocitinib use

6) The count and proportion patients identified with severe hepatic impairment up to 6 months prior to or during treatment with abrocitinib

7) The count and proportion of patients aged <12 years on the index date

PFIZER CONFIDENTIAL

Abrocitinib B7451085 NON-INTERVENTIONAL STUDY PROTOCOL Version 2.0, 23 May 2024 8) The count of proportion of patients with an estimated starting dose > 100mg/day, and a description of the duration of use (median and IQR)

All proportions will be reported with 95% CIs.

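### The only age indicator counts under-12s at every index date, so in four countries first dispensings at ages 12–17 before the March 2024 label extension go unflagged

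*Protocol*

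**What the plan says.** The age objective in Protocol section 8.2 reads "Indicators of adherence to no use in patients aged < 12 years, and" and the analysis that serves it, section 9.7.1 item 7, is "The count and proportion of patients aged <12 years on the index date". Neither carries a calendar condition.

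Section 7 gives the label history. The authorisation of 09 December 2021 was "for the treatment of moderate to severe AD in adults who are candidates for systemic therapy". Then: "On 21 March 2024, the indication for abrocitinib marketing authorization for the EU was expanded to adolescents 12 years and older".

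Section 9.2.1 opens inclusion on country-specific dates ("01 Mar 2022, Sweden; 09 Mar 2022, Denmark; 31 Jul 2022, France; 30 Jan 2023, Spain; 05 April 2024, Hungary") and closes it in December 2026. It also states: "The date of the first dispensing of abrocitinib will be the index date". Section 9.2.2 has no exclusion criteria, so patients of any age enter at any date in the window. Section 9.7.2 repeats the main analyses with the start moved back to 09 December 2021, the SmPC issue date.

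**The concern.** The research question in section 8.1 is whether use follows the SmPC, the prescriber's brochure and the DHPC. The amendment table in section 5 justifies the under-12 cut-off as the correct age for off-label use, given the adolescent indication. On section 7's own dates, that reasoning holds only from 21 March 2024. A 15-year-old with a first dispensing in Sweden in 2023 is in the study population and was outside the indication on that day, yet item 7 does not pick that patient up.

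At stake is whether the study can report off-label use by age for the years before the extension. As planned, it can do so only below age 12.

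**Working it through.** The protocol gives no figure of its own on this point, so the check is a comparison of dates.

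**Inputs**
- Label extension: 21 March 2024 (section 7).
- Country start dates: section 9.2.1.
- Study end: the protocol says only December 2026. I take 31 December 2026 and test 1 December below.
- Sensitivity-analysis start: 09 December 2021 (section 9.7.2).

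**Formula**
- Pre-extension days = days from the start date through 20 March 2024.
- Total days = days from the start date through 31 December 2026, both ends counted.
- Share = pre-extension days / total days.

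For Sweden, 01 March 2022 to 29 February 2024 is 731 days (2024 is a leap year), and 1–20 March adds 20, giving 751. The total is 1461 days (01 March 2022 to 28 February 2026) plus 306 days (01 March to 31 December 2026), giving 1767. The share is 751/1767 = 42.5%.

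| Analysis | Start | Pre-extension days | Total days | Share |
|---|---|---|---|---|
| Sweden | 01 Mar 2022 | 751 | 1767 | 42.5% |
| Denmark | 09 Mar 2022 | 743 | 1759 | 42.2% |
| France | 31 Jul 2022 | 599 | 1615 | 37.1% |
| Spain | 30 Jan 2023 | 416 | 1432 | 29.1% |
| Hungary | 05 Apr 2024 | 0 | 1001 | 0% |
| Sensitivity analysis | 09 Dec 2021 | 833 | 1849 | 45.1% |

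**Effect of the assumed end date.** Ending on 1 December 2026 removes 30 days from each total: Sweden 751/1737 = 43.2%, Denmark 743/1729 = 43.0%, France 599/1585 = 37.8%, Spain 416/1402 = 29.7%, sensitivity analysis 833/1819 = 45.8%. No share moves by as much as one percentage point.

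**Is the group counted elsewhere?** Of the eight items in section 9.7.1, only item 7 looks at young age; the age criterion in item 3 is 65 years or older. Baseline age is to be reported by country, but no 12–17 group split at 21 March 2024 is planned. Section 9.7.2 moves the start date and leaves the cut-off unchanged.

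**Patients affected.** This cannot be calculated. The protocol gives no expected user numbers by age or by period.

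**The case against.** The strongest reply is that item 7 matches its objective exactly. Section 7 also ties the under-12 band to a named potential risk, impaired bone growth and development with off-label use, so the indicator can be read as tracking the current risk plan rather than auditing each day's label. The protocol nowhere says that adherence is judged against the label in force on each index date, and the SmPC it cites is the 2024 version. Section 7 gives part of the purpose as deciding whether the programme needs amending, and for that, past use at ages now authorised has limited value. Finally, age and index date are collected, age bands are usual SAP content, and section 9.7.1 lets the SAP modify the plans.

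Part of this stands. There is no mismatch between objective and analysis, and the under-12 count has its own justification and should stay. But section 5 describes the cut-off as the one for off-label use. The other part of the stated purpose, whether programme objectives have been met, covers the years before the extension too. The sensitivity analysis deliberately reaches back to an SmPC that covered adults only. And the cut-off is not left open for the SAP: the protocol fixes it in both the objective and the analysis.

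A reader might go further and infer that the plan records adolescents treated before the extension as adherent. It does not. Item 7 counts those under 12 and gives no label to anyone else. Nor do the documents support saying that adolescents were the likeliest off-label paediatric users, or that the indicator must show almost no non-adherence in those years, because there are no counts to base either statement on.

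**Conclusion.** The point holds for Sweden, Denmark, France and Spain. For 29% to 43% of their calendar accrual time, first dispensings at ages 12–17 were outside the indication that section 7 describes, and no planned indicator would flag them. Hungary is unaffected in the main analysis because its start falls after the extension. The sensitivity analysis lengthens the unflagged period to 45% of its window. Section 9.7.2 exempts no country from the earlier start, so as worded it would bring pre-extension time into Hungary as well.

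The shares rest on the assumed end date, which hardly matters, and on section 7's dates. It is tempting to read them as shares of patients misclassified. They are shares of time, and the number of adolescents involved could be zero or substantial. This is one of eight descriptive indicators; no other indicator and no precision figure depends on it. It should be corrected, but it does not threaten the design.

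**What to change.** Change the measurement only:

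- Classify age against the indication in force at the index date: under 18 years for index dates before 21 March 2024, under 12 years from that date.
- Report the 12–17 count and proportion separately for the two periods, in the main analysis and in the section 9.7.2 analysis from 09 December 2021.
- Keep the overall under-12 count.
- Align the objective in section 8.2, and where it is repeated in the PASS information table and the abstract, with item 7.

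The cost is one sentence and an extra table row per country. Sections 9.2.1 and 9.3 already provide index date and age, so no new data are needed. Small cells are possible in the 12–17 group. Section 9.4 lists year of birth among the French variables, so age near the 18-year boundary may be approximate there, as it would already be near 12.

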9.2.2. Exclusion criteria

There are no exclusion criteria in this study.

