²Cyclosporine, azathioprine, methotrexate, mycophenolic acid, mycophenolate mofetil, dupilumab, tralokinumab; other treatments authorized per country at the time of analysis

³Arbamazepine, rifabutin, enzalutamide, letermovir, phenytoin, rifampicin, apalutamide, rifamycin, rifaximin, rifapentine, bosentan, alpelisib, dabrafenib, efavirenz, fluconazole, flucoxetine, fluvoxamine, ticlopidine

RMM element	Denmark	France	Sweden	Spain ¹	Hungary ^{1, 2}
Complete blood count: absolute lymphocyte count, absolute neutrophil count, platelet count and haemoglobin level	Yes (date performed, hospital labs)	Yes (in/outpatient lab test, no results)	No	Yes if conducted in primary care	Yes (in/outpatient lab test, no results)
Lipid panel: total cholesterol, high- density lipoprotein [HDL], low- density lipoprotein [LDL], and triglycerides [TG])	Yes (date performed, hospital labs)	Yes (in/outpatient lab test, no results)	No	Yes if conducted in primary care	Yes (in/outpatient lab test, no results)
Hepatitis B screening	No	Yes (in/outpatient lab test, no results)	No	No	Yes (in/outpatient lab test, no results)
Hepatitis C screening	No	Yes (in/outpatient lab test, no results)	No	No	Yes (in/outpatient lab test, no results)
TB screening	No	Yes (in/outpatient	No	No	Yes (in/outpatient

 Table 2.
 Availability of RMM elements for evaluation in each country

PFIZER CONFIDENTIAL

RMM element	Denmark	France	Sweden	Spain ¹	Hungary ^{1, 2}
		lab test, no results) or ATC codes (tuberculin skin test)			lab test, no results)
Risk factors for VTE, MACE, malignancy excluding NMSC, NMSC, and serious infection:					
History of VTE	Yes, via in/outpatient diagnoses	Yes, via inpatient diagnoses and outpatients algorithm previously used and validated in a PASS study	Yes, via in/outpatient diagnoses	Yes if recorded in primary care	Yes
Age 65 years or older	Yes	Yes	Yes	Yes	Yes
Dose of > 100 mg/day for patients 65 or older	Yes ³	Yes ³	Yes ³	Yes ⁴	No
History of atherosclerotic disease	Yes, in/outpatient diagnoses	Yes, via inpatient diagnoses and Long term disease registration	Yes, via in/outpatient diagnoses	Yes if recorded in primary care	Yes
Malignancy excluding NMSC, NMSC	Yes, via Danish Cancer Registry or Danish Cancer Registry	Yes, via Long Term Disease registration status, inpatient diagnosis and outpatients treatments for prostatic cancer	Yes, via Swedish Cancer Register	Yes if recorded in primary care	Yes

Table 2. Availability of RMM elements for evaluation in each country

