9.9. Limitations of the Research Methods

Given the use of data sources from 5 distinct EU countries in this study, there will be variability in data captured across the participating countries. For example, data on laboratory tests and vaccinations are not available in Sweden and may be underrecorded in Denmark and France. If only reimbursed services are recorded (e.g., vaccinations, oral contraceptives), some underascertainment will be associated with absence of data on nonreimbursed services. Given the underrecording, absence of a record of a given RMM metric (e.g., hepatitis B, hepatitis C, or TB screening) cannot be interpreted as an indicator of nonadherence for all metrics, and only databases with high completeness of these data should be used in that assessment (Table 2). Similarly, as vaccines recording is based on reimbursement and data is not expected to be complete, the absence of a record is not necessarily indicative of absence of vaccine receipt. Additionally, prescription strength data serves as a proxy for daily dosage in this study; this approach is supported by the absence of scoring on the abrocitinib 200 mg tablets (which would facilitate splitting into separate 100 mg doses), and by reimbursement in Sweden, Denmark, France and Spain (pending for Hungary) for both the 100 mg and 200 mg tablets (i.e. there is no financial justification for a patient to receive a prescription strength of 100 mg to be taken as 2 tablets to achieve 200 mg daily dosage). However, there may be instances where patient dosage does not correspond to the strength prescribed. Dosage data from SIDIAP can only be derived from a combination of WHO Defined Daily Dose (DDD); data from NHIFA on dosage is not available.

Other limitations include uncertainty about identification of abrocitinib in Denmark (however, most newly approved medicines receive hospital procedure codes); incomplete identification of ongoing pregnancies and pregnancies ending in a termination, as they are identifiable only by pregnancy end date; challenges in identifying screening for TB and hepatitis B and C in all participating countries; and potential underestimation of history of atherosclerotic disease given the likelihood of treatment within a primary care setting in all participating countries. Results from participating countries will not necessarily be generalizable to other countries in the EU.

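### The posology indicator (9.7.1, item 8) pools all ages above 100 mg/day, so it cannot by itself show adherence in patients aged 65 or older, the only group to which the protocol elsewhere ties that cut-off

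*Protocol*

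**What the plan says.** Protocol 8.2 sets as one objective "Indicators of adherence to recommended posology (estimated average daily dose"), judged against the SmPC, the prescriber's brochure and the DHPC. The eight analyses in 9.7.1 follow the eight objectives in order, and the one for posology is item 8: "The count of proportion of patients with an estimated starting dose > 100mg/day", together with a summary of how long the drug was used. It names no age group. Section 9.2.2 states that "There are no exclusion criteria in this study", so everyone with a dispensing enters it.

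The same cut-off appears in two other places, both limited by age:

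- Table 2 in 9.3, under the heading for risk factors for VTE, MACE, malignancy and serious infection: "Dose of > 100 mg/day for patients 65 or older". This is the table's only dose row.
- Item 3 of 9.7.1, in the list of risk factors: "estimated dose of >100 mg/day for patients ages 65 or older". The window for the list is "within 6 months prior to initiation of treatment with abrocitinib".

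The protocol does not state the recommended posology. Section 9.9 mentions reimbursement "for both the 100 mg and 200 mg tablets" when it justifies tablet strength as a proxy for daily dose.

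**The concern.** Item 8 is meant to indicate adherence, but the protocol never says for which patients a starting dose above 100 mg/day counts as a departure from posology. Its only age-specific dose statement concerns patients aged 65 or older, and item 8 merges them with everyone else, including the adolescents added to the indication in March 2024.

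Section 7 says the evaluation should show whether the programme met its objectives or needs amendment. If the older group is a minority, the reported proportion mainly describes prescribing to younger patients. It could then look reassuring or alarming whatever happened in the older group.

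**Working it through.** **The protocol's own figure.** The only computed figures are in 9.5. With P = 0.50, half-width e = 0.05 and z = 1.96, n = P(1 − P)z²/e² = 0.25 × 3.8416 / 0.0025 = 384.2, rounded up to 385. This agrees, as do the other eight entries of Table 3. The point does not depend on them, but 385 serves below as a reference size.

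**Inputs.** Let s be the share of initiators aged 65 or older, v the share of that group above 100 mg/day, and u the share of patients under 65 above it. The protocol gives none of these, so all values below are assumptions.

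**Formula.** Item 8 = (1 − s)u + sv. Moving v from 0 to 1 changes item 8 by exactly s, whatever u is.

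| s | u | Item 8 if v = 0% | Item 8 if v = 100% | Change |
|---|---|---|---|---|
| 5% | 30% | 0.95 × 0.30 = 28.5% | 28.5% + 5% = 33.5% | 5 points |
| 10% | 50% | 0.90 × 0.50 = 45% | 45% + 10% = 55% | 10 points |
| 15% | 60% | 0.85 × 0.60 = 51% | 51% + 15% = 66% | 15 points |

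By contrast, hold s = 10% and v = 0% and let u run from 30% to 70%. Item 8 then runs from 0.90 × 0.30 = 27% to 0.90 × 0.70 = 63%, a range of 36 points with no change in the older group.

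**Reading backwards.** For an observed item 8 value P, v can lie anywhere between max(0, (P − (1 − s))/s) and min(1, P/s). With P = 30% or 50% and s = 5%, 10% or 20%, the lower limit is 0 and the upper limit is 1 every time. At the tightest of these, s = 20% and P = 30%, (0.30 − 0.80)/0.20 is negative and 0.30/0.20 exceeds 1. The pooled figure alone therefore fits any value in the older group.

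**Does item 3 fill the gap?** Item 3 reports patients with risk factors and the number of risk factors. It does not promise the proportion above the cut-off among those aged 65 or older. Its window also lies before initiation, when a patient starting at the index date has no abrocitinib dose to measure.

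**Precision after a split at 65.** At 50%, the half-width is 1.96 × √(0.25/n). With 385 patients in total:

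| s | n aged 65+ | Half-width 65+ | n under 65 | Half-width under 65 |
|---|---|---|---|---|
| 5% | about 19 | 22 points | about 366 | 5.1 points |
| 10% | about 39 | 16 points | about 347 | 5.3 points |
| 20% | 77 | 11 points | 308 | 5.6 points |

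The younger row loses almost nothing and the older row is imprecise. The protocol gives no expected numbers by country, so a country with fewer than 385 patients would have wider intervals still.

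**The case against.** The strongest reply is that nothing here conflicts. Table 2 and item 3 use the cut-off as a risk-factor element, and item 8 uses it for a separate posology objective, so one threshold can serve two purposes. That stands, and a reader who infers a contradiction goes further than the text allows.

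A reader might also infer that an all-age cut-off is wrong, or that the posology objective cannot be answered at all. The protocol supports neither. The benchmark is the SmPC, the brochure and the DHPC, and the protocol does not reproduce their dosing. Section 9.9 does not settle it either: it discusses tablet scoring and reimbursement to defend a dose proxy and does not say what is recommended at any age.

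It can also be said that stratification belongs in the SAP, that the stratified-analyses item of the Annex 2 checklist is ticked yes, and that the older group could be recovered if item 3's elements were tabulated singly. This stands in part, since nothing forbids age rows. But 9.7.1 itself fixes the indicator and its population as pooled, the checklist tick cites no section, and item 3 promises no element-level table. What the indicator means, and for whom, is better settled before results are seen.

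Finally, the 5 to 15 points restate a mixture identity under assumed shares. That is true. They show how weakly the pooled figure reflects the older group, and they are not a forecast.

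**Conclusion.** The point holds in a limited form. The only posology analysis is an all-age proportion, and on its own it cannot show adherence in the one group to which the protocol otherwise ties the cut-off. At an assumed 5% to 15% share aged 65 or older, the full range from none to all above the cut-off in that group is worth 5 to 15 points of the pooled figure. The size depends on that assumed share. The direction does not, because a subgroup of share s can move the total by at most s.

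No view is taken on which dose is recommended for anyone, because the protocol does not show it. The study's validity is not in question. This is a worthwhile and inexpensive correction to one indicator.

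**What to change.** - Report item 8 separately for patients under 65 and those 65 or older at the index date, each with count, own denominator and 95% CI. Do this in each country with dose data, so without Hungary, which 9.3 excludes from the dose analyses. Only the split at 65 has support in the protocol's dose statements, so further bands are optional.
- Reconcile item 8 with Table 2, item 3 and the SmPC reference by stating in 9.7.1 for which patients the cut-off is an adherence indicator.
- Keep the pooled row if wanted, but draw no adherence conclusion from it alone.

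The cost is a few table rows and a sentence or two, since age is already collected. The drawback is imprecision in the older row (half-width about 11 to 22 points at 50% if 19 to 77 of 385 patients fall in it) and possible masking of small cells in some countries.
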